9.3.3 Removal of Subjects From Therapy or Assessment

The investigator or subinvestigator may discontinue treating a subject with study treatment or withdraw the subject from the study at any time for safety or administrative reasons. The subject may decide to discontinue study treatment or withdraw from the study at any time for any reason. The reason for discontinuation will be documented. If a subject discontinues study treatment, the subject will complete protocol-specified discontinuation visits and procedures and survival follow-up unless the subject withdraws consent. If a subject withdraws consent, the date will be documented in the source documents.

In Part 2, all subjects will be followed for survival until death every 12 weeks (± 2 week) from the date of discontinuation, except where a subject withdraws consent or the sponsor chooses to halt survival follow-up. The survival follow-up will be continued until discontinuation of the last subject or for up to 2 years after Cycle 1 Day 1 of the last subject enrolled in Part 2, whichever occurs later.

9.3.3.1 Discontinuation Criteria by Subject

If a subject meets any of the following criteria, the investigator will discontinue treating a subject with study treatment.

1. The subject refuses to continue participation in the study or wishes to withdraw consent.
2. Major violations of inclusion or exclusion criteria in the protocol are found after study enrollment.
3. Subject is unable to continue the study due to an adverse event, in the opinion of the investigator or subinvestigator.
4. The subject becomes pregnant.
5. Progressive disease (when the investigator or subinvestigator judges clinical benefit of lenvatinib plus nivolumab is maintained, it can be continued).
6. The investigator or subinvestigator determines that discontinuation in the study is appropriate.

9.4 Treatments

For this study, the study drugs are E7080/lenvatinib and ONO-4538/nivolumab.

9.4.1 Treatments Administered

9.4.1.1 Lenvatinib

Lenvatinib is provided as 4-mg capsule. Lenvatinib will be administered once a day (with or without food) in 4-week cycles at approximately the same time each day. On Day 1 and Day 15 of each cycle, in case concomitantly administered, it will be administered immediately after completion of nivolumab administration.

Starting dose of lenvatinib will be based on baseline BW as follows:

- BW \geq 60 kg — 12 mg QD. Study subjects will be orally administered lenvatinib as three 4-mg capsules.
- BW <60 kg — 8 mg QD. Study subjects will be orally administered lenvatinib as two 4-mg capsules.

9.4.1.2 Nivolumab

Nivolumab injection for intravenous infusion contains 100 mg/10 mL of nivolumab in each vial. Nivolumab will be administered at a dose of 240 mg as an IV infusion over 30 minutes, Q2W (Day 1 and Day 15 of each cycle). Please refer to the current version of the Investigator's Brochure (IB) and instructions for handling of investigational products for complete storage, preparation and administration information for nivolumab.

9.4.1.3 Criteria for Interruption of Treatment, Dose Reduction and Discontinuation of Treatment

9.4.1.3.1 CYCLE 1 (PART 1 ONLY)

1. If DLT occurs:

Relationship of the DLT to lenvatinib and/or nivolumab will be evaluated, then lenvatinib and/or infusion of nivolumab should be interrupted or discontinued immediately. Treatment may be resumed at the same dose level of nivolumab and at 1 lower dose level of lenvatinib if toxicity is resolved to Grade 0–1 (or tolerable Grade 2 for hematologic toxicities and proteinuria in case of lenvatinib) or baseline, when investigator or subinvestigator decides to continue the study.

2. No DLT occurs:

Relationship of the DLT to lenvatinib and/or nivolumab will be evaluated, then lenvatinib and/or nivolumab will be interrupted. Dose adjustments for management of intolerable toxicities will be made according to the guidelines provided in the table below. Lenvatinib and nivolumab should be resumed at the same dose level, and dose reduction is not allowed.

9.4.1.3.2 CYCLE 2 AND ONWARD (AND APPLIES TO CYCLE 1 AND ONWARD OF PART 2)

Relationship to lenvatinib and/or nivolumab will be evaluated, then necessity of dose modification (either or both drugs) will be determined. Dose adjustments for management of intolerable toxicities will be made according to the guidelines provided in the table below.

9.4.1.3.2.1 Criteria for Interruption of Treatment, Dose Reduction, and Discontinuation of Lenvatinib

Dose adjustments for management of intolerable toxicities will be made according to the guidelines shown in Table 2. Lenvatinib dose should be reduced as shown in Table 3. For management of hypertension, refer to Section 9.4.1.4 without consulting the table below.

Table 2 Dose Adjustments of Lenvatinib

Treatment-Related Toxicity ^{a,b}		Dose Adjustment
Hematologic Toxicities and Proteinuria	Grade 3 ^c	Interrupt until resolved to Grade 0-2 or baseline. In the first occurrence, dose should not be changed. In the second occurrence or later, reduce lenvatinib by 1 dose level.
	Grade 4	Interrupt until resolved to Grade 0-2 or baseline. Reduce lenvatinib by 1 more dose level.
Nonhematologic Toxicities	Intolerable Grade 2 ^d	Dose of lenvatinib will be reduced by 1 dose level with or without dose interruption.
	Grade 3 ^{e,f}	Interrupt until resolved to Grade 0-1 or baseline. Reduce lenvatinib by 1 dose level.
	Grade 4 ^{f,g}	Discontinue lenvatinib

a: An interruption of lenvatinib for more than 28 days (due to treatment-related toxicities) will require discussion with the sponsor before treatment can be resumed. During treatment interruption, repeat AEs assessment about every 7 days (until restarting administration).

b: Initiate optimal medical management for nausea, vomiting, diarrhea, and/or hypothyroidism prior to interruption or dose reduction of lenvatinib.

c: Not applicable to abnormal clinical laboratory values that are not clinically significant based on the judgment of the investigator or subinvestigator.

d: Grade 2 toxicities will be determined to be tolerable or intolerable by both the subject and investigator or subinvestigator.

e: Obese subjects with weight loss do not need to return to baseline or Grade 1 weight loss to restart lenvatinib. There should be no weight loss for at least 1 week, and subjects should be started at the lower dose.

f: For asymptomatic Grade ≥ 3 elevations of amylase and lipase, sponsor should be consulted to obtain permission to continue treatment.

g: Excluding laboratory abnormalities judged to be nonlife-threatening, which should be managed as Grade 3.

Table 3 Dose Reduction Recommendations for Lenvatinib

Initial Lenvatinib Dose (mg, QD)	Adjusted Dose To Be Administered (mg, QD)		
	Reduction 1	Reduction 2	Reduction 3
12	8	4	4QOD ^a
8	4	4QOD ^a	

a: 4 mg every other day [QOD]. Any dose reduction below 4 mg every other day must be discussed with the sponsor.

9.4.1.3.2.2 Criteria for Delay of Treatment, Resumption, and Discontinuation of Nivolumab

9.4.1.3.2.2.1 Criteria for Delay of Treatment and Resumption of Nivolumab

Dose adjustments for management of intolerable toxicities will be made according to the guidelines shown in Table 4.

Table 4 Dose Delay and Resuming Dosing of Nivolumab

Treatment-Related Toxicity ^a	Dose Delay Criteria	Criteria to Resume Dosing
Skin-related adverse event	Grade 3	Grade \leq 1 or baseline value
Fatigue	Grade 3	Grade \leq 2
Laboratory abnormality (except for AST/ALT)	Grade 3 (except for amylase or lipase abnormalities that are not associated with symptoms or clinical manifestations of pancreatitis)	Grade \leq 1 or baseline value (T-Bil: baseline CTCAE Grade or normal)
AST/ALT	Baseline AST/ALT is within normal limits: Grade \geq 2. Baseline AST/ALT is Grade 1: Grade \geq 3. Baseline AST/ALT is Grade 2: \geq two-fold of baseline value or \geq 8x ULN	Baseline CTCAE Grade or normal
Pulmonary toxicity, diarrhea, or colitis	Grade \geq 2	Baseline
Others	Grade \geq 2	Grade \leq 1 or baseline value (Endocrinopathies adequately controlled with only physiologic hormone replacement may resume treatment.)

ULN: upper limit of normal.

a: A delay of nivolumab for more than 6 weeks will require sponsor's approval before treatment can be resumed.

9.4.1.3.2.2.2 Discontinuation Criteria of Nivolumab

Nivolumab treatment should be discontinued for the following AEs related to nivolumab:

- Any Grade 2 uveitis, eye pain or blurred vision that does not respond to topical therapy and does not improve to Grade 1 severity within the re-treatment period or requires systemic treatment.
- Any Grade 3 uveitis, pneumonitis, bronchospasm, hypersensitivity reaction, or infusion reaction.
- Any Grade 3 thrombocytopenia lasting >7 days or associated with bleeding.
- Any Grade 3 AE lasting >7 days, with the exceptions of skin, laboratory abnormalities, endocrinopathies adequately controlled with only physiologic hormone replacement.
- Any hepatotoxicity as below:

- AST or ALT $>10 \times \text{ULN}$ for >2 weeks
- AST or ALT $>15 \times \text{ULN}$
- For subjects with total bilirubin $\leq \text{ULN}$ at baseline: total bilirubin $>5 \times \text{ULN}$
- For subjects with increased bilirubin at baseline: total bilirubin $>8 \times \text{ULN}$
- Any Grade 4 AE or laboratory abnormality, except for the following
 - Neutropenia <7 days
 - Lymphopenia or leukopenia
 - Amylase or lipase abnormalities that are not associated with symptoms or clinical manifestations of pancreatitis.
 - Isolated electrolyte imbalances/abnormalities that are not associated with clinical sequelae and are corrected with supplementation/appropriate management within 72 hours of their onset.
 - Endocrinopathy adverse events that are adequately controlled with physiologic hormone replacement.

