31. Women of childbearing potential or men of impregnate potential who don't agree that both the subject and her partner will use the following methods of contraception for periods from before informed consent to during the clinical study and 5 months later (for male subjects 30 days) from last administration of study drug. For contraception method, subject must agree to use any 2 of the following methods: vasectomy or condom for a male subject or partner, bilateral tubal ligation, diaphragm, intrauterine device, or use of oral contraception from at least 28 days before starting the study treatment for a female subject or partner.
32. Participants who have received a live/attenuated vaccine within 28 days of first dose of study drugs

Study Treatments

Study drug in the study defines as E7080/lenvatinib and ONO-4538/nivolumab.

Lenvatinib

Lenvatinib is provided as 4-mg capsule. Lenvatinib will be administered once a day (with or without food) in 4-week cycles at approximately the same time each day. On Day 1 and Day 15 of each cycle, in case concomitantly administered, it will be administered immediately after completion of nivolumab administration.

Starting dose of lenvatinib will be based on baseline BW as follows:

- BW \geq 60 kg — 12 mg QD. Study subjects will be orally administered lenvatinib as three 4-mg capsules.
- BW <60 kg — 8 mg QD. Study subjects will be orally administered lenvatinib as two 4-mg capsules.

Nivolumab

Nivolumab is a clear to opalescent, colorless to pale-yellow liquid. Nivolumab injection for intravenous infusion is supplied as vials. Nivolumab will be administered as a dose of 240 mg as a 30-minute IV infusion, Q2W.

Study Treatment Dose Modification

1. Cycle 1 (Part 1 only)

a. If DLT occurs:

Relationship to lenvatinib and/or nivolumab will be evaluated, then lenvatinib and/or infusion of nivolumab should be interrupted or discontinued immediately. Treatment may be resumed at same dose level of nivolumab and at 1 lower dose level of lenvatinib if toxicity is resolved to Grade 0-1 (or tolerable Grade 2 for hematologic toxicities and proteinuria in case of lenvatinib) or baseline, when investigator or subinvestigator decides to continue the study.

b. No DLT

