Nonhematologic Toxicity (Hepatotoxicity)	
 • Clinical deterioration manifested by drug-related hepatic decompensation (eg, encephalopathy etc.) • AST or ALT > 15×ULN • AST/ALT >10.0×ULN lasting > 7 days or associated with clinical symptom • Total bilirubin > 5×ULN (for subjects with increased bilirubin at baseline, total bilirubin > 8×ULN)
Nonhematologic Toxicity (General)	
 • Grade 4 nonhematologic toxicity (excluding laboratory abnormalities with no clinical significance) • Grade 3 gastrointestinal perforation, thromboembolic event, uveitis, pneumonitis, bronchospasm, hypersensitivity reaction, infusion reaction, or wound dehiscence requiring treatment • Grade 3 toxicities lasting >3 days despite optimal supportive therapies (excluding abnormal laboratory values with no clinical significance or controllable hypertension) • Grade 2 uveitis, eye pain, or blurred vision that does not respond to topical therapy and does not improve to Grade 1 within the re-treatment period or requires systemic treatment • Eight or more days of dose interruption of lenvatinib as a result of lenvatinib or nivolumab treatment-related toxicity during Cycle 1*

* For reasons other than toxicity, this will not be considered as a DLT. In this situation, the relevant subject will be excluded from assessments of DLT and new subject will be added. DLT was determined after discussions among the sponsor, the investigator, and the sponsor's responsible medical officer. An efficacy and safety evaluation advisor may be consulted for the consideration as needed.

9.1.2 Part 2

If the dose level is confirmed to be tolerable in Part 1, an additional 20 HCC subjects with no prior systemic therapy will be enrolled. At least 5 subjects (BW \geq 60 kg) treated with

lenvatinib 12 mg QD and at least 5 subjects (BW <60 kg) treated with lenvatinib 8 mg QD will be included.

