9.4.1.4 Management of Hypertension

Guidelines for assessment and management of hypertension are summarized as follows. CTCAE v4.03 grading for hypertension will be based on BP measurements only (and not on the number of antihypertensive medications).

1. When blood pressure (BP) is elevated (systolic BP ≥ 140 mmHg or diastolic BP ≥ 90 mmHg), BP measurement should be repeated at least 5 min apart. In this case, BP assessment is defined as the mean value of two measurements at least 5 minutes apart.
2. When systolic BP ≥ 140 mmHg or diastolic BP ≥ 90 mmHg is observed in the 1st BP assessment, the 2nd BP assessment should be repeated at least 30 min apart. The 2nd BP assessment is defined as the mean value of two measurements at least 5 minutes apart. For previously normotensive subjects, monotherapy with one of the classes of antihypertensives should be started when systolic BP ≥ 140 mmHg or diastolic BP ≥ 90 mmHg is firstly observed on the 2nd BP assessment. For those subjects already on antihypertensive medication, the dose of the current agent may be increased, if appropriate, or one or more agents of a different class of antihypertensives should be added.
3. If systolic BP ≥ 160 mmHg or diastolic BP ≥ 100 mmHg continues despite optimal management of hypertension, lenvatinib should be interrupted and resumed according to Table 3 at a dose of one-dose level reduction only when systolic BP ≤ 150 mmHg and diastolic BP ≤ 95 mmHg and the subject has been on a stable dose of antihypertensive medication for at least 48 hours.
4. If systolic BP ≥ 160 mmHg or diastolic BP ≥ 100 mmHg recurs despite the optimal management of hypertension, one-dose level reduction should be attempted.
5. Discontinue lenvatinib administration when Grade 4 hypertension (life-threatening) is present.

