9.4.1.6 Management Algorithms for Immuno-Oncology Agents

The following groups of AEs will be managed by “Appendix 3 Management Algorithms” found in the current nivolumab IB:

- Gastrointestinal
- Renal
- Pulmonary
- Endocrinopathy
- Skin
- Neurological

Please note that management algorithms of this protocol for the hepatic AEs are changed as below:

- If AST or ALT elevation does not improve in 3 to 5 days of dose delay or worsen, methylprednisolone 0.5 to 2 mg/kg or oral steroids equivalent will start.
- If AST or ALT $>8 \times \text{ULN}$ occurs, methylprednisolone 1 to 2 mg/kg or oral steroids equivalent will start immediately.
- Subjects who started steroids should be consulted with the sponsor within 24 hours of corticosteroids initiation. Consultation with gastroenterologist will be recommended.
- If AST or ALT elevation does not improve in 3 to 5 days or worsen, addition of mycophenolate mofetil 1 g twice daily should be considered with the sponsor.

- If AST or ALT elevation returns to 1 grade below, steroids can be tapered over at least 1 month.

As shown in Section 9.4.1.3.2.2.1, if AST or ALT elevation returns to baseline and a subject does not meet nivolumab discontinuation criteria (Section 9.4.1.3.2.2.2), nivolumab can be resumed.

[figure not shown]

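### Part 1 Cycle 1: the permission to resume treatment after a resolved DLT does not except events that require a permanent stop elsewhere in the protocol

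*Protocol*

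**What the plan says.** Protocol 9.4.1.3.1 governs Part 1 Cycle 1. Under item 1, when a DLT occurs, one or both drugs are interrupted or discontinued at once. Then "Treatment may be resumed at the same dose level of nivolumab and at 1 lower dose level of lenvatinib if toxicity is resolved". The event must have returned to Grade 0–1 or baseline (for lenvatinib, tolerable Grade 2 is enough for hematologic toxicity and proteinuria), and the investigator or subinvestigator must decide to go on. The synopsis has the same rule: "Treatment may be resumed at same dose level of nivolumab and at 1 lower dose level of lenvatinib if toxicity is resolved". Neither place says which DLTs call for discontinuation rather than interruption, and neither cites a stop list.

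The stop rules stand elsewhere:

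- **Nivolumab.** Section 9.4.1.3.2.2.2 lists related events for which nivolumab is to be discontinued, among them "Any Grade 3 uveitis, pneumonitis, bronchospasm, hypersensitivity reaction, or infusion reaction".
- **Lenvatinib, general.** Table 2 requires discontinuation for Grade 4 nonhematologic toxicity, subject to footnotes f and g.
- **Lenvatinib, hypertension.** Section 9.4.1.4 item 5: "Discontinue lenvatinib administration when Grade 4 hypertension (life-threatening) is present". That section has no cycle limit.

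The first two are nested under 9.4.1.3.2, whose heading reads "CYCLE 2 AND ONWARD (AND APPLIES TO CYCLE 1 AND ONWARD OF PART 2". For nivolumab after AST/ALT elevation, 9.4.1.6 adds a link that is not limited by cycle: "if AST or ALT elevation returns to baseline and a subject does not meet nivolumab discontinuation criteria (Section 9.4.1.3.2.2.2), nivolumab can be resumed".

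**The concern.** The heading of 9.4.1.3.2 covers Part 1 from Cycle 2 and Part 2 from Cycle 1. The only setting it leaves out is Part 1 Cycle 1, where the combination is first tested and DLTs are counted. In that setting item 1 gives an open permission to resume.

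Read as written, a subject could be re-treated after an event for which the same protocol orders a permanent stop in every setting that the heading covers. At stake is the safety of the few subjects who have a DLT. The DLT definitions and the tolerability rule are not affected.

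**Working it through.** No figure in the plan bears on this point, so the check sets the texts side by side.

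**Step 1. Overlap between DLTs and the nivolumab stop list.** Table 1 has 5 hematologic + 4 hepatic + 5 general = 14 entries. If the event is related to nivolumab, five match 9.4.1.3.2.2.2 by wording or threshold:

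| Table 1 entry | What else in the protocol reaches Part 1 Cycle 1 |
|---|---|
| Grade 3 thrombocytopenia, prolonged or with bleeding | Nothing found |
| AST or ALT >15×ULN | 9.4.1.6 makes resumption depend on the stop list |
| Bilirubin >5×ULN (>8×ULN if raised at baseline) | Nothing found; the 9.4.1.6 condition is written for AST/ALT |
| Grade 2 eye events | One limb is failure to improve to Grade 1, which largely cannot meet item 1's resolution condition; the systemic-treatment limb remains |
| Named Grade 3 events | Pneumonitis goes to the algorithms in the investigator's brochure (IB) through the pulmonary group |

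The last entry reads "Grade 3 gastrointestinal perforation, thromboembolic event, uveitis, pneumonitis, bronchospasm, hypersensitivity reaction, infusion reaction, or wound dehiscence requiring treatment". Five of its eight events are on the stop list: uveitis, pneumonitis, bronchospasm, hypersensitivity reaction and infusion reaction. Entries that would meet the list only through its general Grade 4 clause, or its clause for Grade 3 events lasting more than 7 days, are not counted.

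So 5 of 14 entries overlap in wording. Removing AST/ALT leaves 5 − 1 = 4 entries with some part not covered elsewhere, and two of those four (eye events, named Grade 3 events) are open only in part.

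**Step 2. Lenvatinib.** One Table 1 entry, Grade 4 nonhematologic toxicity, corresponds to the Table 2 stop. Treatment-related Grade 4 hypertension falls within that entry, because the exception for controllable hypertension belongs only to the entry on Grade 3 toxicity lasting more than 3 days. Section 9.4.1.4 item 3 speaks of interrupting and resuming, so discontinuation in item 5 means a permanent stop. Item 1 would allow a restart one level lower, and the protocol does not say which rule prevails.

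**Step 3. The clearest case.** Nivolumab is given "Q2W (Day 1 and Day 15 of each cycle". A related Grade 3 infusion reaction on Day 1 is a DLT and can resolve before Day 15. Item 1 then permits 240 mg on Day 15, whereas the stop list would end nivolumab. Infusion reactions are not among the six event groups that 9.4.1.6 sends to the IB algorithms.

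**Step 4. Exposure within Cycle 1.** There are two infusions per cycle, on Days 1 and 15. After a DLT that follows the first, at most 2 − 1 = 1 infusion remains, plus lenvatinib for the rest of the 28-day cycle.

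**Step 5. How many subjects.** The automatic finding of tolerability requires 0 or 1 DLT in 6, so at most 1 of 6 subjects enters item 1 on that route. With 2 or more DLTs the question goes to discussion (9.1.1), so that bound does not hold there.

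**The case against.** The best defence is that item 1 only permits, and that its wording includes discontinuation. An investigator who follows a specific stop rule breaches nothing. Several safeguards stand alongside it:

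- The sponsor and its medical officer take part in determining a DLT.
- Part 1 subjects are in hospital until at least Day 15.
- 9.3.3.1 items 3 and 6 allow discontinuation on the investigator's judgment.
- 9.4.1.2 refers to the IB for nivolumab administration, and the IB may address infusion reactions.

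This stands as mitigation. None of the safeguards in the protocol obliges a stop, and the IB is not among these documents.

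The defence does rule out some stronger readings that a reader might infer:

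- *The hypertension rules contradict each other.* They do not. A permission stands beside a specific order with no cycle limit, and a site satisfies both by stopping. What is missing is a statement of precedence.
- *The stop list cannot apply in Part 1 Cycle 1.* That follows from the section numbering in the protocol body. In the synopsis the stop list stands under an unnumbered heading after both cycle items, with no explicit cycle limit, so its scope there is unclear.
- *Five of 14 DLT types are unprotected.* Five is a count of shared wording. Step 1 shows that one is already covered and two are open only in part.
- *The no-DLT branch needs the same correction.* Applying the whole stop list there could force a permanent stop for a clinically insignificant Grade 4 laboratory value that is not a DLT. If that left the subject with fewer than two nivolumab doses, the subject would drop out of the DLT Analysis Set (9.7.1.2). Nor is a lenvatinib restart grade for intolerable Grade 2 toxicity needed. Table 2 gives none in any cycle, the 8-day interruption DLT bounds the wait, and any threshold chosen would be arbitrary.

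**Conclusion.** The point holds as a gap in scope and precedence. In Part 1 Cycle 1 the protocol permits treatment to resume after any resolved DLT, at the investigator's decision, without excepting events that call for a permanent stop elsewhere. The Day 1 infusion reaction shows the consequence most plainly.

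The size is small: at most one further infusion within Cycle 1 per affected subject, plus lenvatinib for the rest of the cycle, and at most 1 of 6 subjects if the dose passes automatically. The documents do not say whether the situation arose.

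The conclusion assumes that the section headings define scope, that the event is judged related to the drug concerned, and that no source outside these documents, the IB in particular, already forbids resumption.

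Practical value is limited. The reason recorded for version 7.0 treats the long-term Part 1 trough data as already sufficient, so Part 1 Cycle 1 appears complete. The text would matter for a lower-dose cohort, which 9.1.1 allows for, or if it were reused. I would label this a cheap improvement for patient safety.

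**What to change.** Add one sentence to 9.4.1.3.1 item 1 and to the matching synopsis text:

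> After a DLT, nivolumab must not be resumed if the event meets the nivolumab discontinuation criteria (Section 9.4.1.3.2.2.2), and lenvatinib must not be resumed if the event meets the Grade 4 nonhematologic row of Table 2, with its footnotes, or Section 9.4.1.4 item 5.

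Limit it to the DLT branch. Leave the no-DLT branch, Table 1 and the 0-or-1-of-6 rule unchanged. A subject with a Cycle 1 DLT belongs to the DLT Analysis Set whatever the number of nivolumab doses, so the sentence removes nobody from the tolerability assessment and needs no extra subjects, procedures or analyses. The cost is that a few subjects lose the option of rechallenge after a DLT.
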